ICH	International Conference on Harmonisation
ITT	intent-to-treat
LS Mean	least-squares mean
MAPLV	Markedly abnormal post-baseline values
MedDRA	Medical Dictionary for Regulatory Activities
MI	multiple imputation

Abbreviation	Definition
PCS	potentially clinically significant
PERMP	Permanent Product Measure of Performance
PERMP-A	PERMP-number of PERMP problems attempted
PERMP-C	PERMP-number of PERMP problems correctly completed
PMM	pattern mixture model
PP	per protocol
PT	preferred term
RBC	red blood cell
ROC	Receiver Operating Characteristic
SAE(s)	serious adverse event(s)
SAP	statistical analysis plan
SKAMP	Swanson, Kotin, Agler, M-Flynn, and Pelham Rating Scale
SKAMP-CS	SKAMP-Combined Score
SOC	system organ class
TEAE	treatment-emergent adverse event
WBC	white blood cell
WHO	World Health Organization
WHO DRUG E	World Health Organization – Enhanced Drug Dictionary

1. PURPOSE OF THE STATISTICAL ANALYSIS PLAN

The purpose of the analyses described in this document is to compare the safety and efficacy of dasotraline to placebo in pediatric patients with attention deficit hyperactivity disorder (ADHD).

The statistical analysis plan (SAP) is written with due consideration of the recommendations outlined in the most recent International Conference on Harmonisation (ICH) E9 Guideline entitled Guidance for Industry: Statistical Principles for Clinical Trials [1] and the most recent ICH E3 Guideline, entitled Guidance for Industry: Structure and Content of Clinical Study Reports [2].

This SAP describes the populations that will be analyzed, the subject characteristics parameters, the efficacy parameters, and the safety parameters. The details of the specific statistical methods that will be used will be provided. If additional analyses are required to supplement the planned analyses described in this SAP, they may be completed and will be identified in the clinical study report (CSR). [Table](#), [figure](#), and [listing](#) specifications are provided in separate documents.

2. PROTOCOL SUMMARY

2.1 Study Objectives

The primary objective of this study is to evaluate the efficacy of dasotraline compared to placebo on attention-deficit hyperactivity disorder (ADHD) symptoms in children (6 – 12 years of age) in a laboratory classroom setting.

The secondary objectives are to evaluate the efficacy of dasotraline compared to placebo on ADHD symptoms throughout the day (12 to 24 hours post-dose) in children in a laboratory classroom setting and to evaluate the safety and tolerability of dasotraline using physical examinations, 12-lead electrocardiograms (ECG), vital signs, adverse event (AE) reports, clinical laboratory results, and Columbia – Suicide Severity Rating Scale (C-SSRS) Children’s Assessment.

2.2 Overall Study Design and Plan

This is a randomized, double-blind, placebo-controlled, parallel-group, efficacy and safety study in children with ADHD in a laboratory classroom setting. The study will target 110 subjects (55 per treatment group) in an attempt to have 100 subjects complete the study.

The study will be comprised of 3 periods:

1. Period 1: Screening (up to 35 days) including a 3 - 5 day ADHD medication washout prior to Day -1;
2. Period 2: Double-blind randomized treatment with either dasotraline 4 mg/day or placebo for 14 days (prior to Protocol Amendment 2.0, subjects were also randomized to dasotraline 6 mg/day); and
3. Period 3: End of Study (EOS) Visit (7 days after last dose)

Prior to the start of treatment (Day 1) and following the conclusion of the 14-day double-blind period (Day 15), subjects will undergo a full-day laboratory classroom evaluation during which approximately 12 to 18 subjects will be assessed. Each laboratory classroom day will include seven 30-minute simulated classroom sessions where trained observers will assess subjects using the Swanson, Kotin, Agler, M-Flynn, and Pelham (SKAMP) Rating Scale. In addition during each classroom session, a 10-minute math test (Permanent Product Measure of Performance [PERMP]) will be administered to evaluate sustained attention and effort. The appropriate math level for each subject is determined based on results of the math pretest administered at screening.

The primary efficacy endpoint will be baseline (Day 1) to endpoint (Day 15) change in the SKAMP Combined score (SKAMP-CS).

Safety and tolerability will be monitored throughout the study by physical and neurological examinations, 12-lead ECG, vital signs, AEs, clinical laboratories (hematology, chemistry, and urinalysis), and C-SSRS.

Screening: The screening period will be completed within a maximum of 35 days prior to the first dose of study drug and will begin with acquisition of informed assent by the subject and informed consent from at least one of the subject's parents/legal guardians.

Subjects will be confirmed to have been treated with a methylphenidate for at least 6 weeks prior to Day -7. Subjects will be evaluated by the investigator and confirmed to demonstrate adequate clinical response to prior treatment with methylphenidate based on clinical assessment and informant interview, as well as, review of available medical records. Between Days -9 and -7, the subject's parent/legal guardian will be contacted to complete the ADHD Rating Scale Version IV - Home Version (modified for investigator administration) (ADHD-RS-IV HV), or if the parent/legal guardian cannot be reached, it may be completed when he or she brings the subject on Day -7. On Day -7 subjects will attend a half-day practice laboratory classroom session intended to familiarize them with classroom schedules and procedures related to SKAMP evaluations, PERMP tests, and other planned activities. All subjects will discontinue prior methylphenidate treatment for 3-5 days prior to Day -1 in order to ensure that there is at least a 72 hour washout from methylphenidate prior to the assessment of ADHD symptoms on Day -1. The day before randomization, the subject's parent/legal guardian will be contacted by study site staff in order to confirm clinical worsening of the subject's ADHD symptoms since discontinuation of methylphenidate. Clinical worsening is defined as an ADHD-RS-IV HV total score ≥ 26 and demonstration of at least a 30% worsening in ADHD-RS-IV HV total score since the last assessment and following the minimum 72 hour washout from prior methylphenidate treatment. Subjects who do not demonstrate clinical worsening following washout of methylphenidate will be considered screen failures and not randomized.

[figure not shown]
Double-blind Period: On Day 1 subjects will return to the clinic in the morning and those who meet all inclusion and no exclusion criteria will be randomized (1:1) to receive 4 mg/day dasotraline or placebo and will attend classroom sessions in which they will be evaluated for ADHD symptoms using the SKAMP assessment. During this baseline classroom assessment (Day 1), subjects will be evaluated at regular intervals: approximately 8 AM, 10 AM, 12 PM, 2 PM, 4 PM, 6 PM, and 8 PM. Subjects will begin taking study drug on the evening of Day 1 (with

or without food) and take one dose each evening before bedtime for a total of 14 days. Study drug should be taken at approximately the same time each evening. The first dose of study drug may be administered in the clinic before the subject leaves or at home. On the night (Day 14) before the second classroom day, study drug must be taken at 8 PM plus or minus 30 minutes. During the double-blind period, the clinical site will attempt to contact the subject's parent/legal guardian daily with a reminder to administer study drug. A dosing diary will be provided to the parent/legal guardian to record the date and time of each administration of study drug. On Day 15 subjects will return to the clinic in the morning and classroom sessions will be started at approximately 8 AM, 10 AM, 12 PM, 2 PM, 4 PM, 6 PM and 8 PM to coincide with 12, 14, 16, 18, 20, 22, and 24 hours following the Day 14 dose.

End of Study: Seven (\pm 2) days after the last dose of study drug, all subjects will return to the clinic complete assessments. After the EOS visit, all subjects will be referred for continuation of their care as determined by the investigator. Additionally, for subjects who complete the study or discontinue for tolerability or lack of efficacy reasons, the sponsor will provide support for approved ADHD medication costs for up to 3 months after participation in the study, if deemed medically appropriate by the subject's healthcare provider.

A study schematic is presented in Figure 1. Details of the study assessments and other procedures to be performed at each visit are presented in Appendix 14.1, Schedule of Assessments. If necessary, subjects may return to the clinic at any time for an unscheduled visit. The timing of events during a sample laboratory classroom day is provided in Appendix 14.2.

Figure 1: Study Schematic

2.3 Study Population

The subject population includes males and females ranging from 6 to 12 years of age, and in concert with standard practice guidelines, will be required to have a diagnosis of ADHD established by a comprehensive psychiatric evaluation that reviewed Diagnostic and Statistical Manual for Mental Disorders, Fifth Edition (DSM-5) criteria for ADHD (inattentive, hyperactive, or combined presentation). The specific inclusion and exclusion criteria can be found in the protocol, Sections 8.1 and 8.2.

2.4 Method of Assigning Subjects to Treatment Groups

After successfully meeting study entry criteria, subjects will be randomly assigned in a 1:1 ratio to 1 of the 2 following treatments:

- 4 mg/day dasotraline (N = approximately 55 subjects)
- Placebo (N = approximately 55 subjects)

Under previous versions of the protocol, subjects were also randomly assigned to a third treatment group in a 1:1:1 overall ratio: 6 mg/day dasotraline (N = approximately 20 subjects randomized before protocol was amended). An Interactive Response System (IXRS) will be used to manage randomization on Day 1 and, if necessary, for emergency unblinding of treatment assignment during the study. The IXRS is an integrated web based subject and drug management system.

Study medication will be assigned by an IXRS based on the randomization schedule. The IXRS will generate instructions on which medication number to assign to a subject.

2.5 Treatment Regimens

Under supervision from the subject's parent/legal guardian, subjects will self-administer the study drug on an outpatient basis for 14 days beginning the evening of Day 1. Study drug will be taken at approximately the same time each evening. The first dose of study drug may be administered in the clinic before the subject leaves or at home. On Day 14, the night before the second classroom day, study drug must be taken at 8 PM plus or minus 30 minutes. All study medication doses will consist of one 4 mg or placebo capsule per day taken by mouth.

2.6 Sample Size Determination

A post-baseline least square (LS) mean of 18.66 in mean SKAMP-CS obtained from an average of 7 assessments collected across the 12-hour classroom day was observed for the placebo group in a similarly designed study (Wigal 2013) [3]. It is assumed that the dasotraline group will have approximately 20% improvement in mean SKAMP-CS

for dasotraline 4 mg/day versus placebo. The treatment mean difference in change from baseline is therefore assumed to be 4.0 units (effect size of 0.8) versus placebo on mean SKAMP-CS with a common standard deviation of 5 units for dasotraline 4 mg/day. The two-sample t-test with equal variance procedure using nQuery Version 7.0 was utilized for the sample size/power calculation. A total of 100 subjects (50 each for the dasotraline 4 mg/day and placebo groups) will provide at least 95% power to detect statistically significant treatment differences for the dasotraline dose group versus placebo in the primary endpoint at a 5% significance level (2-sided).

The study will target approximately 110 subjects randomized in an attempt to have 100 subjects complete the trial. In addition, approximately 20 other subjects were randomized to dasotraline 6 mg/day under previous versions of the protocol. The total number of subjects randomized in this study will be approximately 130.

3. GENERAL ANALYSIS, REPORTING, AND PROGRAMMING CONVENTIONS

This section discusses general policies to be employed in the analysis and reporting of the data from the study. Departures from these general policies may be given in the specific detailed sections of this SAP. When this situation occurs, the rules set forth in the specific section take precedence over the general policies.

All continuous study assessments will be summarized by treatment group (4 mg/day dasotraline, 6 mg/day dasotraline, combined dasotraline [4 mg/day + 6 mg/day], and placebo) and time point (as applicable) using descriptive statistics (n, mean, median, standard deviation, minimum, and maximum). All categorical study assessments will be summarized by treatment group and time point (as applicable) using frequency counts and percentages. All study data will be listed by subject, treatment group, and time point (as applicable).

Hypothesis testing, unless otherwise indicated, will be 2-sided and performed at the 5% significance level. When confidence intervals are presented, they will be 2-sided with a confidence coefficient of 95%. P-values will be reported to 3 decimal places if greater than 0.001. If less than 0.001, '<0.001' will be displayed. P-values and significance levels will be reported as 0.05 rather than .05. Due to the removal of the 6 mg/day dasotraline treatment group from the study under Protocol Amendment 2.0, the hypothesis testing of 6 mg/day dasotraline versus placebo will be conducted as an exploratory analysis only and will be summarized separately from the 4 mg/day treatment group.

Data will be summarized based on the recorded visit; no visit windowing will be performed.

No preliminary rounding will be performed; rounding will only occur after analysis. To round, the digit to right of last significant digit will be considered: if <5 then round down, if ≥ 5 then round up. Means and medians will be presented with one more decimal place than the precision of the data. Standard deviations will be presented with two more decimal places than the precision of the data. Percentages will be presented with one decimal place. Minimums and maximums will be presented with the same precision as the original data.

Medical history and AEs will be coded using the Medical Dictionary for Regulatory Activities (MedDRA) Version 19.0. Medications will be coded with the World Health Organization – Enhanced Drug Dictionary (WHO DRUG E, 2016 Q1 version).

All analyses will be performed using the SAS System® version 9.3 or higher.

The following general programming conventions will apply:

Exposure days: (Last dosing date – first dosing date + 1)

Compliance: [(Number of doses taken)/(number of doses planned)]*100

Duration days: (End/resolution date – start/onset date +1)

Study day: (Date of interest – first dosing date + 1) if date of interest is on or after the first dosing date. (Date of interest – first dosing date) if date of interest is before the first dosing date.

4. ANALYSIS POPULATIONS

The 3 analysis populations are defined below. Subjects will be analyzed based on the treatment to which they are randomly assigned. Identification of the subjects to be included in each analysis population will be determined prior to database unblinding. The database will be locked and unblinded after the SAP is signed and authorized, there are no outstanding data issues, and the final analysis populations are imported into the study database.

4.1 Intent-to-Treat Population

The Intent-to-Treat (ITT) population is defined as all subjects who are randomized. The ITT population will be used for the efficacy analyses. Efficacy data will be analyzed according to the treatment the subject was randomized to receive.

4.2 Safety Population

The safety population includes all subjects who are randomized and receive at least 1 dose of study medication. All safety analyses will be performed using the safety population, which includes subjects that had been treated with dasotraline 6 mg/day.

Safety data will be analyzed according to the treatment the subject actually received, regardless of the treatment to which the subject was originally randomized. For subjects who inadvertently received treatment from more than one treatment arm due to site conduct error, the subject will be categorized by the treatment he/she received the most.

4.3 Per-Protocol Population

The per-protocol (PP) population is defined as all subjects from the ITT population without any important protocol deviations (see Section 4.5). This supplemental efficacy population will be used to assess robustness of the primary analysis results.

4.4 Disposition of Patients

Subject disposition will be summarized for all screened subjects, for each treatment group and overall. The following subject disposition information will be presented:

- The number and percentage of patients who were screened, who were screen failures, who were randomized, who completed the study, and who prematurely discontinued from the study
- The number and percentage of patients who discontinued prematurely, by reason for premature discontinuation

- The number and percentage of patients in the ITT, safety, and PP populations

In addition to these summaries, a listing by subject will be provided that shows treatment assignment, patient number, sex, age, race, reason for discontinuation, and any specific comments related to discontinuation.

4.5 Protocol Deviations

Protocol deviations (PDs) will be collected during monitoring visits. Protocol deviations will be placed, but not limited to, into the following categories: prohibited concomitant medications, dosing, enrollment inclusion/exclusion criteria, laboratory, non-compliance, and others which are deemed to be study PDs. Each instance of a PD will be reviewed and determined to be important or minor before the study DBL.

A summary of important PDs will be provided as number (%) of subjects with at least 1 important PD and number (%) of subjects in each category in all randomized subjects. A listing by subject will also be provided that will include all PDs, deviation date, type, and any specific comments related to the deviation.

The following conditions, if met, would constitute an important PD. As such, any subject meeting one or more of these conditions would be omitted from the PP population. Important PDs are not limited to the list below. All protocol deviations within the monitoring report and the clinical database will be reconciled and adjudicated by the clinical team after the study is complete for the identification of all other important PDs.

	Category	Explanation
1	No proof of randomization or subjects mistakenly randomized	At Visit 4, there is no randomization number indicated on CRF field or subject mistakenly assigned randomization number.
2	Subject is non-compliant	Subject is not lost to follow-up and is <75% or >125% compliant with study drug at any point in the study.
3	Prohibited medications taken	Subject took any of the prohibited medications listed in Section 10.3.1 of the protocol during the study from screening through the EOS visit, unless the medication is clinically adjudicated as permissible.
4	Treated subject who did not meet inclusion/exclusion	Subject failed one or more of the inclusion or exclusion criteria listed in Section 8 of the

	criteria	protocol, but continued in the double-blind period of the study.
5	Subject tests positive for substance abuse	Subject has one or more positive urine drug screen test at any visit during the course of the study.
6	Subject is unblinded during study	Subject is unblinded to treatment at any time during the course of the study.
7	Subject receives incorrect treatment	Subject's actual treatment received does not match randomized planned treatment.

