8.1. Subject Inclusion Criteria

The subjects who fulfill the following criteria will be included in the study.

1. Subject is 6 - 12 years old, inclusive at screening and randomization.
2. At least one of the subject's parents/legal guardians must give written informed consent, including privacy authorization, prior to study participation. The subject will provide informed assent prior to study participation.
3. Subject meets Diagnostic and Statistical Manual of Mental Disorders Fifth Edition (DSM-5) criteria for a primary diagnosis of ADHD (inattentive, hyperactive, or combined presentation) at screening established by a comprehensive psychiatric evaluation that reviews DSM-5 criteria and confirmed using the Schedule for Affective Disorders and Schizophrenia for School-Age Children-Present and Lifetime version (K-SADS-PL) at screening.
4. Subject is currently on a treatment regimen of a methylphenidate formulation within the approved labeled dose range for ADHD for at least 6 weeks prior to Day -7 with the same dose level for at least 1 week immediately prior to Day -7. Note: If any doses of methylphenidate were missed during the week prior to Day -7, the subject's eligibility will be discussed with the Medical Monitor.
5. In the opinion of the investigator, methylphenidate is well tolerated and clinically effective based on clinical assessment and informant interview, as well as, review of available medical records. Note: The ADHD Rating Scale Version IV - Home Version (modified for investigator administration) (ADHD-RS-IV HV) will be administered at Screening by the investigator to inform clinical evaluation.
6. Subject is male or a non-pregnant, non-lactating female.
7. Subject, if female, must not be pregnant or breastfeeding, and if ≥ 8 years of age must have a negative serum pregnancy test at screening.
8. Female subjects of childbearing potential and male subjects with female partners of childbearing potential must practice true abstinence (consistent with lifestyle) and must agree to remain abstinent or agree to use an effective and medically acceptable form of birth control, from the time of informed consent/assent to at least 14 days after the last dose of the study drug has been taken. See [Section 10.5](#) for information on acceptable methods of birth control.

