10.3.1. Prohibited Medications

Subject must not have taken any of the following medications within the timeframe listed:

- Anticonvulsants for seizure control within 2 years prior to screening
- Antipsychotic medication within 6 months prior to screening
- Herbal or complementary treatments, eg, St. John's Wort, within 7 days prior to Day 1
- Any antidepressant medication (eg, bupropion, SSRI/ SNRI, tricyclic, etc) within 7 days prior to Day 1
- MAO inhibitor within 21 days prior to Day 1
- Amphetamine-based product as treatment for ADHD within 6 weeks prior to the start of screening
- Non-methylphenidate product as treatment for ADHD within 6 weeks prior to the start of screening.

All subjects will discontinue their methylphenidate regimen for 3 - 5 days prior to Day -1 in order to ensure that there is at least a 72-hour washout from methylphenidate prior to the assessment of ADHD symptoms on Day -1. Treatment with any ADHD medication is prohibited during the washout period. In addition, all subjects are required to refrain from other prohibited medications for at least 7 days, unless otherwise specified, prior to the first dose of study drug.

Use of any of the following medications is not permitted during the study from screening through the EOS visit:

- Lithium (any lithium preparation or formulation)
- Alpha-2 adrenergic receptor agonists (including clonidine and guanfacine), modafinil, armodafinil, atomoxetine, or any stimulant class agent (methylphenidate- or amphetamine-based)
- Antidepressant medications (eg, bupropion, SSRI/SNRI, MAO inhibitor, tricyclic, etc)
- Anticonvulsant medications (eg, phenytoin, carbamazepine, lamotrigine, valproic acid, etc) and antipsychotic medications
- Pseudoephedrine-containing medications
- Medications with significant effect on blood pressure or heart rate. Intermittent use of asthma treatments is permitted but should be discussed with the medical monitor.
- Sleep aids with the exception of melatonin
- Diphenhydramine except topical formulations
- Herbal or complementary treatments, eg, St. John's Wort
- CYP2B6 substrates or inhibitors or inducers of CYP2B6 (see [Section 23](#), Appendix IV).

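### Important deviation 3 (SAP 4.5) catches the methylphenidate that inclusion 4 requires and runs past the Day 15 endpoint, so per-protocol membership rests on an adjudication with no stated criteria

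*SAP*

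**What the plan says.** The PP set is defined in SAP 4.3 as "all subjects from the ITT population without any important protocol deviations", and its stated purpose is to check the robustness of the primary result. SAP 4.5 lists the important deviations and says that "any subject meeting one or more of these conditions would be omitted from the PP population".

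Item 3 of that list reads "Subject took any of the prohibited medications listed in Section 10.3.1 of the protocol during the study from screening through the EOS visit", followed by the exception "unless the medication is clinically adjudicated as permissible". The SAP does not say what makes a medication permissible.

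Protocol 10.3.1 supplies the list and the same window: "Use of any of the following medications is not permitted during the study from screening through the EOS visit". Among the entries is "any stimulant class agent (methylphenidate- or amphetamine-based"). The same section has all children stop methylphenidate 3 to 5 days before Day -1. Inclusion criterion 4 in Protocol 8.1 reads "Subject is currently on a treatment regimen of a methylphenidate formulation within the approved labeled dose range for ADHD for at least 6 weeks", counted back from Day -7, with a stable dose in the last week before Day -7.

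The primary endpoint is complete at the last classroom session on Day 15 (Protocol 6.1 and 7.1). The end-of-study (EOS) visit is on Day 21 ± 2 (Protocol Table 2).

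**The concern.** A PP exclusion rule should pick out children whose conduct departed from the protocol in a way that could affect the endpoint. Item 3 misses that target at both ends of its window.

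At the start, it catches a drug that the protocol requires. The condition therefore does not separate compliant from non-compliant children, and the separating is left to the adjudication clause. Protocol 15.3.3 says that the SAP will define important deviations in detail. On this item the SAP defers the definition again.

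At the end, it catches medication taken after the outcome has been measured. A child who takes any listed drug between the last Day 15 session and EOS, whether a resumed stimulant or a sleep aid, meets the condition although the SKAMP data are complete. If children with poor symptom control resume treatment sooner, exclusion on this ground depends on the outcome.

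At stake is whether the PP result can be reproduced from the written rules, and whether it is a clean check on the ITT result.

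**Working it through.** **1. Dates side by side.** SAP section 3 counts days with no Day 0.

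| Event | Day | Source |
|---|---|---|
| Visit 1 | -35 to -8 (SAP: -35 to -10) | Protocol 11.5.1.1; SAP Appendix 14.1 |
| Methylphenidate required up to | -7 | Protocol 8.1, inclusion 4 |
| Methylphenidate stopped | -6 to -4 | Protocol 10.3.1: -1 - 5 = -6; -1 - 3 = -4 |
| Last SKAMP session | 15 (8 PM) | Protocol 7.1 |
| EOS visit | 19 to 23 | Protocol Table 2: 21 - 2 = 19; 21 + 2 = 23 |

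**2. Start of the window.** Visit 1 falls before Day -7 for every child, and methylphenidate continues to Day -6 at the earliest stop. Under the protocol's dates the overlap between the prohibited window and scheduled use is at least 2 days (Day -8 to -6) and at most 31 days (Day -35 to -4). It is never zero, so all correctly enrolled children meet the condition before the exception is considered.

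**3. What the exception does.** About 110 children are to be randomized to dasotraline 4 mg/day or placebo. If no exemption were granted, 0 of about 110 would remain in the PP set. If the required pre-washout use is exempted, this cause removes 0. The text fixes neither result. The exception also attaches to the medication and does not mention timing. Read literally, declaring methylphenidate permissible could also cover its use during double-blind treatment, which a PP analysis should exclude.

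**4. End of the window.** 19 - 15 = 4 and 23 - 15 = 8, so the window runs 4 to 8 days past the endpoint (nominally 21 - 15 = 6).

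**5. Effect on the PP contrast.** Let a fraction f of an arm be removed, and let g be the removed children's mean minus the kept children's mean. Then

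mean(all) - mean(kept) = f × g.

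Higher SKAMP is worse, so removing poorly controlled children (g > 0) improves that arm's PP mean by f × g. In the placebo arm this shrinks the drug-placebo difference; in the dasotraline arm it widens it. The documents give neither f nor g. As an assumption, purely to show scale, take g equal to one planning SD (5 units): f = 10% gives 0.10 × 5 = 0.5 units and f = 20% gives 0.20 × 5 = 1.0 unit, against a planned difference of 4.0.

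**6. Effect on precision.** The plan's own figure first: 50 per arm, difference 4.0, SD 5, two-sided 5%. The noncentrality is 4 / (5 × √(1/50 + 1/50)) = 4.0 on 98 degrees of freedom. Power is 97.7% by the two-sample t-test, consistent with the stated minimum of 95%. With assumed PP losses:

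| Loss | Both arms (n per arm) | Placebo only (dasotraline 50) |
|---|---|---|
| 10% | 96.4% (45) | 97.1% |
| 20% | 94.2% (40) | 96.2% |
| 30% | 91.0% (35) | 94.8% |
| 40% | 86.1% (30) | 92.8% |

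Moderate losses cost little power. The problem is reproducibility and possible selection, not sample size.

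**The case against.** A reader might infer that item 3, applied as written, empties the PP set. The documents do not support that. The same sentence lets a medication be judged permissible, and 10.3.1 itself schedules methylphenidate until washout, so use that the protocol requires is not naturally a deviation. SAP 4.5 names the category as prohibited concomitant medications, and under SAP 5.1 a drug stopped before Day 1 counts as prior medication only. An empty set is not a realistic outcome. These passages are context rather than a cure, because item 3 still says that its window opens at screening.

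A reader might also infer that the PP comparison will be biased, perhaps in favour of dasotraline. That is not supported either. No restart rate is given, by arm or overall. Use before EOS is itself prohibited by 10.3.1. Removal is not automatic, because the exception applies here too. In the most obvious scenario, early restarts among poorly controlled placebo children, the PP difference would shrink, which is conservative for superiority.

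The safeguards are real. SAP section 4 fixes population membership before unblinding, and Protocol 15.3.3 says the same for children with important deviations. Exempting a required drug that both arms took before randomization cannot favour either arm. Robustness is also examined by placebo-based imputation and a tipping-point analysis (SAP 7.1.1.2).

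Two things remain. Fixing membership before unblinding hides the treatment arm, but neither document says that adjudicators are kept from the Day 15 scores, which exist by the time post-Day 15 use is judged. And nothing in the safeguards explains why medication taken after the endpoint should count against valid endpoint data.

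**Conclusion.** The point holds in a limited form. Every correctly enrolled child meets the condition in item 3, and PP membership depends on an adjudication with no written criteria. The exclusion window overruns the endpoint by 4 to 8 days and can discard valid Day 15 data for events that cannot have changed them. Such removal may depend on outcome; direction and size cannot be known from the documents.

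This rests on the visit days in Protocol Table 2 and on children following inclusion 4 and the washout as scheduled. The consequence stops at the supplemental PP analysis. The primary ANCOVA is on the ITT population (SAP 7.5.1) and is unaffected. The item should be corrected before unblinding, but it is no threat to the primary conclusion.

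**What to change.** Amend item 3 in SAP 4.5 before unblinding:

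- **(a)** State that methylphenidate required by inclusion 4 and taken before the scheduled washout is not an important deviation, and that use from the start of washout onward is, up to the cut-off in (b).
- **(b)** End PP exclusion under this item at the last SKAMP session on Day 15. Continue to record and list later use as a protocol deviation, without removing the child from the PP set.
- **(c)** Leave the start of the window and the existing look-back periods for all other 10.3.1 medications as they are.

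Part (c) matters because starting the whole window at washout would open a gap. Protocol 10.3.1 requires other prohibited drugs to be stopped at least 7 days before first dose, that is by Day -7, whereas washout starts on Day -6 to -4. The gap would be 1 to 3 days.

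The sponsor should also reconcile the 10.3.1 list with inclusion 4 and with the discontinuation schedule in the same section. How that is done is a protocol matter and is not proposed here.

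When making the edit, check item 5 as well. It covers a positive urine drug screen at any visit, and a screen that includes amphetamines is taken at EOS, so a child kept under (b) could still be dropped there.

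The cost is a sentence or two of SAP wording. No new data and no change to the primary analysis are needed.
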